4.2. Dose-Limiting Toxicity

For guiding dose-escalation decisions, DLTs will be defined based on TEAEs or abnormal laboratory values that meet DLT criteria that occur up to Day 21 of Cycle 1 for Schedule A and Day 28 of Cycle 1 for Schedule B. AE severity will be graded according to National Cancer Institute (NCI) Common Terminology Criteria for Adverse Events version 5.0 (CTCAE v5.0). DLTs will be defined separately for hematologic, non-hematologic, and hepatic events.

In addition to conventional Cycle 1 DLTs to guide escalation, cumulative toxicity and tolerability for all cohorts will be considered and may be utilized to inform dose escalation.

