4.2.1. Hematologic Dose-Limiting Toxicity

Hematologic DLT is defined as follows:

- Grade 4 neutropenia lasting > 7 days
- \geq Grade 3 febrile neutropenia Grade 4 thrombocytopenia, irrespective of duration
- Grade 3 thrombocytopenia associated with clinically significant bleeding
 - \geq Grade 3 hemolysis

The following events will be specifically **excluded** from the definition of hematologic DLT:

- ≥ Grade 3 lymphopenia
- Grade 3 anemia that is not associated with other clinically significant complications

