4.2.2. Non-hematologic Dose-Limiting Toxicity

Non-hematologic DLT is defined as any \geq Grade 3 non-hematologic event, including Grade 3 ocular symptoms and signs.

The following events will be specifically excluded from the definition of non-hematologic DLT:

- Grade 3 electrolyte abnormality that lasts < 72 hours, is not otherwise associated with clinical complications, and responds to medical intervention
- Grade 3 fever that lasts < 72 hours and is not associated with hemodynamic compromise
- Grade 3 nausea or vomiting that lasts < 72 hours and responds to medical intervention
- Grade 3 or greater amylase and/or lipase elevation that is not associated with clinical or radiographic evidence of pancreatitis requiring hospitalization
- Grade 3 gastrointestinal AEs of diarrhea, constipation, abdominal pain, cramping, dyspepsia, or dysphagia that resolves to ≤ Grade 1 or baseline within 72 hours with maximal supportive care
- Grade 3 fatigue that lasts < 72 hours

Note: The following Grade 2 non-hematologic AEs may also be considered as DLTs:

- Grade 2 AEs that are prolonged inordinately, based upon the medical judgment of the investigator, and/or lead to permanent discontinuation of study drugs due to participant intolerance
- Hepatic laboratory abnormalities meeting Hy's law criteria (described within Section 4.2.3)
- Eye pain or reduction in visual acuity that does not respond to topical ophthalmic therapy and does not improve to Grade 1 within 14 days of initiation of topical ophthalmic therapy, or that requires systemic treatment

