4.4. Dose Escalation Rules

Dose escalation will use a conventional 3 + 3 design. Participants who are not evaluable for safety for the full DLT evaluation period for reasons other than study drug-related toxicity may be replaced in the same dose-level cohort.

If 0 of the first 3 participants treated at a given dose level experience a DLT during the DLT evaluation period, the dose will be escalated, and 3 participants will be enrolled and treated at the next higher dose level.

If 1 of the first 3 participants treated at a given dose level experiences a DLT, then 3 additional participants will be enrolled at that dose level to further assess the safety of IMGC936.

- If ≥ 1 of these 3 additional participants (ie, ≥ 2 of the 6 participants) experience a DLT, it will be concluded that the MTD has been exceeded, and 3 participants will be enrolled and treated at the next lower dose level.
- If 0 of the 3 additional participants (ie, ≤ 1 of the 6 participants) experience a DLT, then the dose will be escalated, and 3 participants will be enrolled at the next higher dose level.

If ≥ 2 of the first 3 participants treated at a given dose level, or ≥ 2 of 6 participants treated at a given dose level, experience a DLT, then it will be concluded that the MTD for IMGC936 has been exceeded at that dose level, and all subsequent participants will be treated at the next lower dose level.

For participants being treated at a dose level subsequently determined to exceed the MTD for a given cohort of the study, the dose of IMGC936 will be reduced to the next lower dose level as summarized in Table 2. Following these rules for dose escalation, the MTD/MAD will be the highest dose administered at which the incidence of DLT is < 33%.

Dose escalation to the next dose level is permitted only after the participants enrolled in the current dose cohort have completed the DLT evaluation period and the safety data have been reviewed by the sponsor medical monitor and the investigators participating in the study. Evaluation of safety data from each cohort will include an assessment of the proportion of participants who receive planned doses, and the percentage of participants that require dose reductions or dose discontinuations for toxicity. All available data from participants both during and beyond the DLT evaluation period will be considered when making dose escalation decisions and in determination of the RP2D.

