At the discretion of the sponsor, dose escalation may be stopped before an MTD is reached. In this case, the MAD may be chosen based on an assessment of PK, safety, and response data. An MTD does not have to be reached to expand a dose cohort if the available data demonstrate that a lower dose level may provide antitumor activity while minimizing potential risk.

At the discretion of the sponsor, any dose escalation cohort at a dose level not exceeding the MTD may be expanded to a maximum of 15 participants for further evaluation of safety, PK, antitumor activity, to facilitate selection of the RP2D. Intermediate dose levels, not exceeding the MTD, may also be explored. Following determination of the RP2D, tumor-specific expansion cohorts may be opened in tumor types selected from those enrolled in dose escalation.

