4.5.1. Dose Delays

Participants who experience toxicity should have study drug held pending assessment, management, and resolution of the toxicity. If the toxicity is assessed as unrelated to study drug or does not meet DLT criteria, study drug may be restarted at the previous dose and schedule, after consultation with the medical monitor. The toxicity should have resolved prior to reinstitution of study drug per guidelines outlined in Section 7. Reinstitution of study drug shall be conducted as follows:

• Dose delays of up to 21 days are allowed for participants who experience toxicity. This may include 1 missed dose of IMGC936 on Schedule A and 2 missed doses on Schedule B. The procedures at the originally scheduled missed visit should be performed as soon as possible with study drug reinstituted as if no delay had occurred, picking up at the day where the interruption occurred per the schedule in Appendix 1 and Appendix 2. Participants who have a dose delay of > 21 days may restart study drug with discussion and approval of the sponsor.

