5.4. Guidelines for Study Drug Discontinuation

Participants who tolerate study drug may continue to receive the study drug, as specified in the protocol, until any one of the following conditions are met:

- Progressive disease (PD) Objective progression per RECIST v1.1 or clinical progression as determined by investigator
 - Participants who experience PD by RECIST v1.1 should discontinue study drug.
 However, participants who have experienced clinical benefit may continue the treatment if agreed upon between the sponsor and the investigator
- AE requiring study drug discontinuation including, but not limited to, the following events:
 - Study drug-related ≥ Grade 3 cardiac event

- Study drug-related Grade 4 non hematologic event
- DLT during dose-escalation window (DLT period)
- Pregnancy
- Death
- Investigator decision
- LTFU
- Major protocol deviation requiring study drug discontinuation
- Participant declining further treatment
- Participant decision to withdraw consent for study
- The sponsor, investigator, or regulatory agency terminate the study

If the investigator decides that the participant should be withdrawn from the study or from dosing for any reason other than disease progression, the sponsor or its designee must be alerted in a timely manner by completing the appropriate eCRFs.

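### Protocol 4.2.1 has no anemia criterion, so read literally an isolated, non-hemolytic Grade 4 or 5 anemia in Cycle 1 is not a DLT

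*Protocol*

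**What the plan says.** Protocol 4.2 sets separate DLT definitions for hematologic, non-hematologic and hepatic events.

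- **Hematologic (4.2.1).** Five criteria: Grade 4 neutropenia beyond 7 days, febrile neutropenia of Grade 3 or higher, Grade 4 thrombocytopenia of any duration, Grade 3 thrombocytopenia with significant bleeding, and hemolysis of Grade 3 or higher. Two exclusions follow: lymphopenia of Grade 3 or higher, and "Grade 3 anemia that is not associated with other clinically significant complications".
- **Non-hematologic (4.2.2).** "Non-hematologic DLT is defined as any" non-hematologic event of Grade 3 or higher, with listed exceptions.
- **Hepatic (4.2.3).** Transaminase, bilirubin and Hy's law criteria only.

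The DLT count drives Protocol 4.4. With 0/3, or 1/6 after expansion, the dose goes up. Two or more DLTs in 3 or 6 mean that the MTD is exceeded, and "the MTD/MAD will be the highest dose administered at which the incidence of DLT is < 33" per cent. Section 5.4 lists a DLT in the evaluation window, and a drug-related Grade 4 non-hematologic event, among the reasons to stop drug.

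Two provisions allow wider judgment. In 4.2, "cumulative toxicity and tolerability for all cohorts will be considered and may be utilized to inform dose escalation". In 4.4, "All available data from participants both during and beyond the DLT evaluation period will be considered when making dose escalation decisions". The sponsor may also halt early: "At the discretion of the sponsor, dose escalation may be stopped before an MTD is reached".

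SAP 3.2.1 repeats the 3 + 3 rules and SAP 7.2 plans a DLT listing. Neither defines a DLT.

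**The concern.** The anemia exclusion is an exception to a list that would not have captured anemia anyway. It has a purpose only if anemia that is more severe, or complicated, was meant to be a DLT. The two exclusions also differ: lymphopenia is excluded at every grade from 3 upward, anemia only at Grade 3 and only when uncomplicated. This points to an inclusion line left out. The intent is an inference; the missing line is not.

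Two rules depend on the DLT label: the escalation and MTD count in 4.4, and the discontinuation line in 5.4. Grade 4 thrombocytopenia of any duration is a DLT while Grade 4 anemia is not, although SAP 7.2 labels Grade 4 as life threatening or disabling. Two people could score the same event differently, which a predefined DLT list is meant to prevent.

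**Working it through.** The plan states no figure on this point, so there is none to reproduce.

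**Step 1. Does any provision count the event?** Take an isolated, non-hemolytic Grade 4 anemia in Cycle 1.

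| Provision | Does it capture the event? |
|---|---|
| 4.2.1 list | No. Hemolysis is the only red-cell criterion, and there is no general Grade 4 line |
| 4.2.1 exclusions | Not excluded, but an exclusion cannot include |
| 4.2.2 | No. Non-hematologic only |
| 4.2.3 | No. Hepatic only |
| 5.4 Grade 4 line | No. Non-hematologic only |
| 5.4 DLT line | No, because the event is not a DLT |
| 7.7 | No. It covers lymphopenia, neutropenia and thrombocytopenia, with no anemia rule |
| SAP 3.2.1, 7.2 | No DLT definition |

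A Grade 5 event is likewise absent from the DLT definitions.

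In the text copy I read, two of the 4.2.1 bullets run together (febrile neutropenia and Grade 4 thrombocytopenia). Nothing suggests that an anemia bullet was lost.

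**Step 2. Effect on the 3 + 3 decision.** No event rate is needed. The inputs are the 4.4 boundaries.

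| Observed | Count as written | Count if anemia were a DLT |
|---|---|---|
| 1 isolated Grade 4 anemia in the first 3, no listed DLT | 0/3, escalate | 1/3, enroll 3 more |
| 2 such anemias in the first 3, no listed DLT | 0/3, escalate | 2/3, MTD exceeded |
| 1 listed DLT and 1 such anemia in 6 | 1/6 = 16.7%, escalate | 2/6 = 33.3%, MTD exceeded |

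**Step 3. Illustration with assumed rates.** Neither document gives a DLT or anemia rate, so these rates are assumptions. With per-participant DLT probability p and q = 1 − p, the 3 + 3 rule gives

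P(escalate) = q³ + 3pq² × q³.

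If scored DLTs have rate s and unscored Grade 4 or 5 anemia has rate a, independently, counting both gives p = 1 − (1 − s)(1 − a).

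| s | a | p if counted | P(escalate) if counted | Drop from as-scored |
|---|---|---|---|---|
| 15% | 0% | 0.1500 | 81.4% | 0 |
| 15% | 1% | 0.1585 | 79.6% | 1.7 points |
| 15% | 2% | 0.1670 | 77.9% | 3.5 points |
| 15% | 5% | 0.1925 | 72.5% | 8.9 points |
| 20% | 0% | 0.200 | 70.9% | 0 |
| 20% | 1% | 0.208 | 69.1% | 1.7 points |
| 20% | 2% | 0.216 | 67.4% | 3.5 points |
| 20% | 5% | 0.240 | 62.2% | 8.7 points |

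Check of the first row: 0.85³ + 3(0.15)(0.85⁵) = 0.6141 + 0.1997 = 0.8138.

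At each assumed pair of rates the drop is an upper bound, because it treats the count as mechanical and ignores the data review in 4.2 and 4.4.

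**The case against.** The strongest reply is that this is a drafting slip with an obvious meaning and several safeguards. Much of that stands.

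- The exclusion makes sense only if worse anemia counts, and no document shows anyone scoring Grade 4 anemia as a non-DLT.
- Consideration of the data is not optional. Section 4.4 permits escalation only after the medical monitor and investigators have reviewed safety, including dose reductions and discontinuations for toxicity. Only the use made of cumulative toxicity is discretionary (4.2).
- A Grade 3 or higher non-hematologic event alongside the anemia, such as a hemorrhage or cardiac event, can be a DLT under 4.2.2, and hemolysis is listed already. Only isolated, non-hemolytic anemia falls through.
- The list of adverse events in 5.4 is not exhaustive, and investigator decision is a separate reason to stop.
- Schedule A escalation is largely past: 7 mg/kg was given (4.1.1), and SAP 7 summarizes a combined 6 mg/kg group as the recommended dose. Schedule B opens only on the Cohort Review Committee's recommendation, and the documents do not show that anyone was enrolled on it.

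What does not stand is that these safeguards close the gap. None of them makes the event a DLT, so the count and the MTD percentage still omit it.

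Three stronger readings are tempting and not supported. A reader might infer that escalation would proceed blindly past a life-threatening anemia; the mandatory review makes that unlikely. A reader might infer that the participant would resume at full dose. Section 4.5.1 says only that, where a toxicity "does not meet DLT criteria, study drug may be restarted at the previous dose and schedule, after consultation with the medical monitor", and it expects resolution first; 4.5 also allows a reduction. A reader might cite the generic scale in 12.1.6 for the meaning of Grade 4, but that scale is for events not contained in CTCAE.

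**Conclusion.** The point holds as a gap in the text. Under the literal wording, an isolated, non-hemolytic Grade 4 or 5 anemia in Cycle 1 adds 0 to the DLT count, and a Grade 4 event meets neither the DLT line nor the Grade 4 non-hematologic line in 5.4. At the boundary this changes the decision from MTD exceeded (2/6) to escalate (1/6).

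The demonstrated size is that reversal and nothing more. The percentage-point figures rest on assumed rates, independence and a mechanical count; the real effect is smaller and may be zero. The documents do not support any inference that a past escalation decision or the 6 mg/kg dose is wrong. The prospective effect is mainly on Schedule B (B1 to B4), if it is opened. Severity is minor to should-fix: a safety rule that works against its own evident intent, with a one-line remedy.

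**What to change.** At the next amendment, add anemia of Grade 4 or higher to the 4.2.1 inclusion list, to apply prospectively, and keep the Grade 3 exclusion. In the same line, the sponsor should state whether Grade 3 anemia with clinically significant complications is a DLT, as the exclusion implies.

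An exception for anemia clearly unrelated to study drug may be reasonable, since 5.1 sets platelet and neutrophil floors but no hemoglobin floor. No other 4.2.1 criterion has such an exception, and it brings judgment back in. If it is wanted, the medical monitor and investigators should decide each case and document the decision.

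Separately, check once the Cycle 1 hemoglobin and adverse event data already collected, and report whether any such event occurred, without rescoring past decisions.

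The cost is one protocol line, with sponsor and IRB/IEC approval (16.1), and one look at existing data. The downside is that a participant who meets the new criterion would stop study drug under 5.4.

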4.2.2. Non-hematologic Dose-Limiting Toxicity

Non-hematologic DLT is defined as any \geq Grade 3 non-hematologic event, including Grade 3 ocular symptoms and signs.

The following events will be specifically excluded from the definition of non-hematologic DLT:

- Grade 3 electrolyte abnormality that lasts < 72 hours, is not otherwise associated with clinical complications, and responds to medical intervention
- Grade 3 fever that lasts < 72 hours and is not associated with hemodynamic compromise
- Grade 3 nausea or vomiting that lasts < 72 hours and responds to medical intervention
- Grade 3 or greater amylase and/or lipase elevation that is not associated with clinical or radiographic evidence of pancreatitis requiring hospitalization
- Grade 3 gastrointestinal AEs of diarrhea, constipation, abdominal pain, cramping, dyspepsia, or dysphagia that resolves to ≤ Grade 1 or baseline within 72 hours with maximal supportive care
- Grade 3 fatigue that lasts < 72 hours

Note: The following Grade 2 non-hematologic AEs may also be considered as DLTs:

- Grade 2 AEs that are prolonged inordinately, based upon the medical judgment of the investigator, and/or lead to permanent discontinuation of study drugs due to participant intolerance
- Hepatic laboratory abnormalities meeting Hy's law criteria (described within Section 4.2.3)
- Eye pain or reduction in visual acuity that does not respond to topical ophthalmic therapy and does not improve to Grade 1 within 14 days of initiation of topical ophthalmic therapy, or that requires systemic treatment

4.2.3. Hepatic Dose-Limiting Toxicity

Hepatic DLTs will be defined as follows:

- Any elevation of one or more transaminases $> 8 \times$ the institutional reference laboratory upper limit of normal (ULN) irrespective of duration
- Any Grade 3 elevation of one or more transaminases > 5.0–8.0 × ULN that does not resolve to Grade 2 (ie, > 3.0–5.0 × ULN) within 7 days and Grade 1 (ie, > ULN–3.0 × ULN) within 14 days.
- Grade 3 elevation of total bilirubin that is $> 5 \times$ the ULN irrespective of duration
- Any Grade 3 elevation of total bilirubin > 3.0–5.0 × ULN that does not resolve to Grade 2 (ie, > 1.5–3.0 × ULN) within 7 days and Grade 1 (ie, > ULN–1.5 × ULN) within 14 days.
- Any event meeting criteria for Hy's law as follows (all 3 features):
 - Aspartate aminotransferase (AST) and/or alanine aminotransferase (ALT) $> 3 \times ULN$
 - Concurrent elevation of total bilirubin > 2 × ULN without initial evidence of cholestasis
 - No alternative etiology can be identified

4.3. Expansion Phase Safety Monitoring

Safety will be evaluated continuously and in aggregate in the expansion cohorts. Safety assessments will be based on all TEAEs and abnormal laboratory values. If at any time \geq 33% of at least 3 participants who received study drug in an expansion cohort experience a study drug—related TEAE leading to discontinuation, enrollment will be paused within that cohort and may also be paused in ongoing cohorts at the discretion of the sponsor. If it is determined that the clinical investigation should be halted due to an unacceptable participant risk, the study must be terminated after appropriate consultation between the sponsor and investigators.

4.4. Dose Escalation Rules

Dose escalation will use a conventional 3 + 3 design. Participants who are not evaluable for safety for the full DLT evaluation period for reasons other than study drug-related toxicity may be replaced in the same dose-level cohort.

If 0 of the first 3 participants treated at a given dose level experience a DLT during the DLT evaluation period, the dose will be escalated, and 3 participants will be enrolled and treated at the next higher dose level.

If 1 of the first 3 participants treated at a given dose level experiences a DLT, then 3 additional participants will be enrolled at that dose level to further assess the safety of IMGC936.

- If ≥ 1 of these 3 additional participants (ie, ≥ 2 of the 6 participants) experience a DLT, it will be concluded that the MTD has been exceeded, and 3 participants will be enrolled and treated at the next lower dose level.
- If 0 of the 3 additional participants (ie, ≤ 1 of the 6 participants) experience a DLT, then the dose will be escalated, and 3 participants will be enrolled at the next higher dose level.

If ≥ 2 of the first 3 participants treated at a given dose level, or ≥ 2 of 6 participants treated at a given dose level, experience a DLT, then it will be concluded that the MTD for IMGC936 has been exceeded at that dose level, and all subsequent participants will be treated at the next lower dose level.

For participants being treated at a dose level subsequently determined to exceed the MTD for a given cohort of the study, the dose of IMGC936 will be reduced to the next lower dose level as summarized in Table 2. Following these rules for dose escalation, the MTD/MAD will be the highest dose administered at which the incidence of DLT is < 33%.

Dose escalation to the next dose level is permitted only after the participants enrolled in the current dose cohort have completed the DLT evaluation period and the safety data have been reviewed by the sponsor medical monitor and the investigators participating in the study. Evaluation of safety data from each cohort will include an assessment of the proportion of participants who receive planned doses, and the percentage of participants that require dose reductions or dose discontinuations for toxicity. All available data from participants both during and beyond the DLT evaluation period will be considered when making dose escalation decisions and in determination of the RP2D.

At the discretion of the sponsor, dose escalation may be stopped before an MTD is reached. In this case, the MAD may be chosen based on an assessment of PK, safety, and response data. An MTD does not have to be reached to expand a dose cohort if the available data demonstrate that a lower dose level may provide antitumor activity while minimizing potential risk.

At the discretion of the sponsor, any dose escalation cohort at a dose level not exceeding the MTD may be expanded to a maximum of 15 participants for further evaluation of safety, PK, antitumor activity, to facilitate selection of the RP2D. Intermediate dose levels, not exceeding the MTD, may also be explored. Following determination of the RP2D, tumor-specific expansion cohorts may be opened in tumor types selected from those enrolled in dose escalation.

4.5. Guidelines for Dose Modification

Dose modifications are allowed for toxicity according to the guidelines in Section 7.

Dose reductions of study drug are allowed for participants experiencing significant toxicity, or an underlying condition that may warrant dose reduction, but are considered to be receiving clinical benefit by the investigator. The investigator should contact the sponsor to discuss the appropriate dose of study drug based on the safety profile and evidence of antitumor activity. A dose reduction by 1 dose level may be allowed, if considered appropriate, rather than study drug discontinuation. The participant must be discontinued from study drug if more than 2 dose reductions are required. Sponsor approval must be obtained in advance of dose reduction of study drug.

